7.6 REPORTING PROCEDURES

7.6.1 ADVERSE EVENT REPORTING

The occurrence of an AE or SAE may come to the attention of study personnel during study visits and interviews of a study participant presenting for medical care, or upon review of subject questionnaires. Any medical condition that is present at the time that the participant is screened will be considered as baseline and not reported as an AE. However, if the study participant's condition deteriorates at any time during the study, it will be recorded as an AE. UPS will be recorded in the data collection system throughout the study. Changes in the severity of an AE will be documented to allow an assessment of the duration of the event at each level of severity to be performed. AEs characterized as intermittent require documentation of onset and duration of each episode. At each study visit, the investigator will inquire about the occurrence of AE/SAEs since the last visit. Events will be followed for outcome information until resolution or stabilization.

The FDA and IRB will receive notification of any UP or SAE within 24 hours of discovery by the primary investigator. All SAEs will be followed until satisfactory resolution or until the site investigator deems the event to be chronic or the adherence to be stable. The study sponsor will be responsible for notifying FDA of any unexpected fatal or life---threatening suspected adverse reaction as soon as possible but in no case later than 7 calendar days after the sponsor's initial receipt of the information.

The study investigator shall complete an Unanticipated Adverse Device Effect Form and submit to the study sponsor and to the reviewing IRB as soon as possible, but in no event later than 7 working days after the investigator first learns of the effect. The study sponsor is responsible for investigating and reporting the results of such evaluation to FDA and to all reviewing IRBs and participating investigators within 10 working days after the sponsor first receives notice of the effect.

A sponsor who conducts an evaluation of an unanticipated adverse device effect under 812.46(b) shall report the results of such evaluation to FDA and to all reviewing IRB's and participating investigators within 10 working days after the sponsor first receives notice of the effect. Thereafter the sponsor shall submit such additional reports concerning the effect as FDA requests (21 CFR 812.150(b)(1)).

The following information should be provided when reporting an AE:

- Subject identification (subject number and initials)
- Event description including observed symptoms
- Medical history related to event
- Event onset date and time
- Depth of injections
- Interventions implemented to treat event
- Event outcome (with resolution date and time if applicable)
- Relatedness to study product or procedure
- Seriousness of event
- Study treatment information such as number of injections, date of injections, name of product injected, volume injected, injection tool (needle) etc.

7.6.2 REPORTING OF PREGNANCY

If it is discovered that a subject is pregnant, the subject will discontinue any interventions.

7.7 STUDY HALTING RULES

Administration of the study agent will be halted when two SAEs determined to be related are reported. The primary investigator will notify the IRB and FDA and investigators immediately when the second

serious adverse event is reported, and enrollment screens will stop accepting new study participants. The study sponsor will inform the FDA of the temporary halt and the disposition of the study.

Additionally, enrollment and treatment into the study will be temporarily halted if the Sponsor receives a SAE for a vascular embolic event that lead to skin necrosis, vision loss, stroke, pulmonary or cardiac complications or death and is determined by the Investigator to be directly or possibly related to the study device or injection procedure. The SAE will be investigated by the Sponsor. If the Sponsor's investigation concludes:

- The SAE was unanticipated, directly related to the study product or device injection procedure, and presents an unreasonable risk to study subjects, the study will be terminated. The IRB and FDA will also be notified if the study is prematurely terminated due to safety concerns.
- If the SAE does not meet the above criteria, then enrollment in the study will continue.

7.8 SAFETY OVERSIGHT & CLINICAL MONITORING

An independent medical expert (medical monitor) will advise the study investigator and monitor participant safety. The role of the Medical Monitor is to 1) Review all AEs on a regular basis throughout the trial; 2) be available to advise the investigators on trial-related medical questions or problems, and 3) evaluate cumulative participant safety data and make recommendations regarding the safe continuation of the study. The Medical Monitor will remain blinded throughout the conduct of the clinical trial unless unblinding is warranted to optimize management of an adverse event or for other safety reasons. Clinical site monitoring is conducted to ensure that the rights and well-being of human subjects are protected, that the reported trial data are accurate, complete, and verifiable, and that the conduct of the trial follows the currently approved protocol/amendment(s), with GCP, and with applicable regulatory requirement(s).

An assessment of pain as a safety endpoint will be done using a quantitative tool to assess pain 30 minutes after treatment, and during the follow up visits.

An independent medical expert (medical monitor) will advise the study investigator and monitor participant safety. The role of the Medical Monitor is to 1) Review all AEs on a regular basis throughout the trial; 2) be available to advise the investigators on trial-related medical questions or problems, and 3) evaluate cumulative participant safety data and make recommendations regarding the safe continuation of the study. The Medical Monitor will remain blinded throughout the conduct of the clinical trial unless unblinding is warranted to optimize management of an adverse event or for other safety reasons. Clinical site monitoring is conducted to ensure that the rights and well-being of human subjects are protected, that the reported trial data are accurate, complete, and verifiable, and that the conduct of the trial follows the currently approved protocol/amendment(s), with GCP, and with applicable regulatory requirement(s).

8 STATISTICAL CONSIDERATIONS

8.1 DESCRIPTION OF STATISTICAL METHODS

This is a randomized clinical study. Continuous data will be expressed as means with standard deviations. The p-value for statistical significance will be 0.05. For the primary objective, the test is one-tailed.

Confidence intervals (CIs) will be two-tailed and constructed at a confidence level of 95%. Statistical tests will be performed at a significance level of 5%, and p-values will be two-sided, unless otherwise specified.

The disposition of subjects will be presented in tables and/or figures as appropriate. The number of screened, treated, completed, and withdrawn subjects will be presented, as well as number of subjects in each analysis population set.

Demographic endpoints, baseline assessments, and subject characteristics will be presented using descriptive statistics by treatment, as appropriate.

The Dataset will be comprised of 15 subjects

8.2 STATISTICAL HYPOTHESES

Primary Endpoint

- The alternative hypothesis is the difference in the mean temperatures on each side of the face is greater than zero
- The null hypothesis is the difference in the mean temperatures on both sides of the face is zero.

Secondary Endpoints

1.

- The alternative hypothesis is the difference in the mean pain, erythema, and comfort scores from one side to the other side is greater than zero
- The null hypothesis is the difference in the mean pain, erythema, and comfort scores from one side to the other side is zero.

All other secondary effectiveness analyses will be done descriptively as appropriate.

8.3 SAFETY ANALYSIS

Safety analysis will be descriptive only.

The number and percentage of subjects reporting each post-treatment symptom will be presented in total and by maximum severity.

A summary of all AEs will be provided, which will include:

- number of subjects with at least one AE and number of events (in total as well as serious AEs)
- number of subjects with at least one related AE and number of events (in total as well as serious AEs)
- number of subjects with at least one mild, moderate, and severe AE and number of events (in total as well as serious AEs)
- number of subjects with at least one unrelated AE and number of events (in total as well as serious AEs)
- number of subjects who did not have an AE

The number of subjects with AEs related to the study product as well as the number of events will be summarized, and action taken for related AEs will also be summarized. Serious AEs will be listed.

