Objectives: Primary Objective: To assess the efficacy of a facial mask in decreasing facial skin temperature after three different aesthetic treatments

Important Secondary Objectives:

1. To determine the safety and incidence of adverse events when using a Velez face mask after 3 different aesthetic treatments
2. To assess the change in the level of pain when using a Velez face mask after aesthetic treatments
3. To assess patient satisfaction with use of a Velez face mask after aesthetic treatments
4. To assess erythema when using a Velez face mask after aesthetic treatments
5. To assess healing time when using a Velez face mask

Primary

Endpoints:

Primary Endpoint:

The difference between the temperature on the mid-cheek (point inferior to the lateral limbus).

Important Secondary Endpoints:

1. The difference in the number of adverse events between the two sides of the face
2. The difference in pain scores on each side of their face as rated by subjects
3. The difference in patient satisfaction scores when rating the procedure on the left and right side of their face
4. The difference in erythema on the left and right side of subject's faces as graded by blinded evaluators doing live assessments 30 minutes after the procedure
5. The difference in healing time on the left and right side of subject's faces as graded by blinded evaluators looking at daily photographs

Population: Healthy adults aged 21 and over living in Palm Beach County, Florida.

Sample Size: 15

Study Sites: [name] &
[name]

Duration: 7 days

Study Agent: Velez Intense Hydration Mask

SCHEMATIC OF STUDY DESIGN

- Total n=15
- Screen potential subjects by inclusion and exclusion criteria

Day 0 Randomization

- Obtain informed consent, randomize into one of the following two groups
- Treatment Group 1 Right Side Velez Intense Hydration Mask
- Treatment Group 2 Left Side Velez Intense Hydration Mask

Day 0 Baseline assessments/ Study Intervention

- Baseline Assessments:
 - Pre-procedure pictures taken with Canfield's imaging system (Front, Right and Left Views)
- Study Intervention:
 - 1st Arm (n=5)

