2.3 POTENTIAL RISKS AND BENEFITS

2.3.1 KNOWN POTENTIAL RISKS & RISK ANALYSIS

Potential risk of the mask includes swelling, itching, pain, dermatitis, erythema, or hypersensitivity.

Potential risk of the cosmetic treatments include swelling, itching, pain, dermatitis, erythema, infection, bleeding or scarring.

To mitigate the risk, patients will be educated on how to properly care for their skin post-procedure and all patients in the ablative arm will be receiving oral antibiotics and antivirals for infection prevention.

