3.2.2 SECONDARY ENDPOINTS

- The difference in the number of adverse events between the two sides of the face
- The difference in pain scores on each side of their face as rated by subjects
- The difference in patient satisfaction scores when rating the procedure on the left and right side of their face
- The difference in erythema on the left and right side of subject's faces as graded by blinded evaluators doing live assessments 30 minutes after the procedure
- The difference in healing time in daily photographs as rated by blinded evaluators

These endpoints will show if the Velez Intense Hydration face mask decreases skin temperature after a cosmetic procedure, if subjects are happy with the use of the mask, and if they provide significant reduction in pain, erythema, and healing time.

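### Section 8.3 plans no symptom or AE summary by procedure arm or by side of the face, so a procedure-specific reaction is diluted and the between-side safety endpoint is not produced

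*Combined protocol and SAP*

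**What the plan says.** The first secondary objective in the Protocol Summary is: "To determine the safety and incidence of adverse events when using a Velez face mask after 3 different aesthetic treatments". The endpoint attached to it, in the Protocol Summary and in section 3.2.2, is: "The difference in the number of adverse events between the two sides of the face".

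Section 8.3 sets out the safety outputs. It opens with "Safety analysis will be descriptive only" and continues: "The number and percentage of subjects reporting each post-treatment symptom will be presented in total and by maximum severity". It then lists counts of subjects and events for all, related, unrelated, mild, moderate and severe AEs, each with serious AEs shown as well. It adds the number of subjects without an AE, the action taken for related AEs, and a listing of serious AEs. Neither procedure arm nor side of the face appears as a breakdown.

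The only summary planned by treatment is in section 8.1: "Demographic endpoints, baseline assessments, and subject characteristics will be presented using descriptive statistics by treatment, as appropriate". AEs are not in that sentence. Section 8.1 also fixes the denominator: "The Dataset will be comprised of 15 subjects".

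**The concern.** The three arms are not interchangeable for safety, on the protocol's own account. Section 2.3.1 says "all patients in the ablative arm will be receiving oral antibiotics and antivirals for infection prevention", a measure that it gives to no other arm as a group. In the study schematic and section 3.1, post-care is Vaseline after the ablative laser and a hydrating serum after the other two procedures. Section 2.1 describes pain and downtime as the limiting feature of ablative resurfacing. A single rate over all subjects is an average over a 5/5/5 mix. If a reaction is confined to one procedure, that average understates it there and overstates it for the other two.

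The side of the face matters at least as much. Section 2.3.1 lists swelling, itching, pain, dermatitis and erythema as risks of both the mask and the procedures. The untreated side is the control that separates the two sources, and the endpoint is defined as the contrast between sides. A table without side cannot show that contrast, either overall or within an arm.

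**Working it through.** The plan states no safety figure, so there is none to reproduce. The check has three parts.

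**1. Is the missing breakdown supplied elsewhere?**
- Section 8.1: the summary by treatment covers demographics, baseline assessments and subject characteristics only.
- Section 8.2: the secondary hypotheses concern pain, erythema and comfort scores. AEs are not mentioned.
- Section 8.6: the remark that each subgroup as well as the combined data will suffice concerns the temperature sample size. The two secondary endpoints to be tested there are not named, but section 8.3 makes safety descriptive, so on a consistent reading the AE difference is not one of them.
- Section 7.5: each AE is recorded with its affected area. The side can therefore be captured, but no output uses it.

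The breakdown is not supplied elsewhere.

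**2. What does the missing arm split do to a rate?**

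Inputs: three arms of 5 (section 3.1), 3 × 5 = 15 (section 8.1). Assumed counts: an AE in all 5 ablative subjects and in none of the other 10.

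Exact (Clopper-Pearson) 95% limits for x events in n subjects are the 0.025 quantile of Beta(x, n − x + 1) and the 0.975 quantile of Beta(x + 1, n − x). For x = n the lower limit reduces to 0.025^(1/n). For x = 0 the upper limit reduces to 1 − 0.025^(1/n).

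- As planned: 5/15 = 33.3%, limits 11.8% to 61.6%.
- Ablative arm: 5/5 = 100%, lower limit 0.025^(1/5) = 47.8%.
- Each other arm: 0/5 = 0%, upper limit 1 − 0.025^(1/5) = 52.2%.
- With the 4 completers per arm that section 4.3 allows for: 4/4 has a lower limit of 0.025^(1/4) = 39.8%, and 0/4 has an upper limit of 60.2%.

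The planned 33% describes none of the three arms. This split is the most extreme one possible, so it shows how large the dilution can be, not what is expected.

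**3. What does the missing side split do to the endpoint?**

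Keep the same 5 affected subjects, with one event each, and consider two assumed cases:
- All events on the mask side: mask 5, control 0, difference 5 − 0 = +5.
- All events on the control side: mask 0, control 5, difference 0 − 5 = −5.

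The headline entries under section 8.3 are identical: 5 subjects with at least one AE, and 5 events. The endpoint has opposite signs. Relatedness counts might hint at the difference, but they rest on the investigator's judgement and are not counts by side.

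The recording rules add a further problem. Section 6.3.3, for the visits on Days 1 to 7, has participant-reported AEs recorded on the mask-assigned side. Section 7.5 asks for all AEs, and the schedule of events has an exam for adverse effects at these visits without restricting it to a side. If section 6.3.3 is followed literally, an assumed reaction on both sides in 5 subjects would be recorded as mask 5, control 0. The difference would be 5 when the true one is 5 − 5 = 0.

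**The case against.** The strongest reply is that this is a gap in table layout with limited consequence. Safety is descriptive, so no test, error rate or decision rule depends on these tables. The halting rule in section 7.7 counts related serious AEs whatever the arm. Serious AEs are listed, affected area is recorded, and with 15 subjects arm-level counts can be recovered from the data. At 5 per arm the intervals are so wide that percentages by arm establish little. All of this stands, and it limits the weight of the point. It does not remove it: non-serious AEs, the likelier kind here, have no planned listing, and control-side follow-up events cannot be recovered if they were never recorded.

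Three stronger readings are tempting, and the documents do not support them.
- A reader might infer that the plan prescribes pooling the arms. No sentence does. Where section 8.3 speaks of totals, the contrast is with severity or seriousness, not with arm, and the AE list is introduced as what the summary will include, so it need not be exhaustive. Pooling arises by omission.
- A reader might infer that the objective promises an incidence after each procedure. The Protocol Summary refers to three different treatments without saying each, and the objectives in section 3.2 refer only to aesthetic procedures. A by-arm display is the natural reading in a trial with three defined arms, but it is not an explicit commitment.
- A reader might infer that arm columns alone would settle mask safety. They would not. A rate of 5/5 in the ablative arm could be laser reaction on both sides. Only the side split addresses the mask.

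**Conclusion.** The point holds as an omission on two axes. Section 8.3 specifies neither an arm breakdown nor a side breakdown, and nothing elsewhere supplies one for safety. The clearer failure is the side: the stated safety endpoint is a between-side difference, and the planned tables do not produce it. The arm split is a weaker claim, resting on the way the objective is framed and on the protocol's different handling of the procedures. It would still let a reaction confined to one procedure be seen.

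The size depends on assumed counts. In the extreme illustration, 33% over 15 subjects stands in for 100%, 0% and 0% by arm. The documents give no expected AE rates from which to say how likely such a pattern is.

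This is a cheap improvement. It does not invalidate the trial, and it does not touch the primary temperature analysis.

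**What to change.** In section 8.3, specify that each post-treatment symptom, the AE summary and the related-AE summary are presented by procedure arm (n=5 each) and in total, and within each of these by mask side and control side. Use the affected area recorded under section 7.5 to assign the side. State the between-side difference in the number of AEs explicitly as an output, so that the endpoint in section 3.2.2 has a table.

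Reconcile section 6.3.3 with section 7.5 so that follow-up AEs are captured on both sides on the same terms.

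Cost: SAP wording, extra table columns and an entry for side at each follow-up visit. The arm split needs no new data, because each subject's arm is known. The side split needs control-side events to be recorded during follow-up. No extra visits are needed. The downside is that arm-level percentages at n=5 are very imprecise. Show counts beside them, keep the display descriptive, and draw no comparison between procedures from it.

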3 STUDY DESIGN, OBJECTIVES, AND ENDPOINTS

3.1 DESCRIPTION OF THE STUDY DESIGN

- A Prospective, Multi-Arm, Split-Face, Randomized Clinical Trial
- 2 Study Centers
- Study agent: Velez Intense Hydration Mask
- Study Intervention on Day 0
- Live evaluations by Blinded Evaluators on Day 0
- Daily photographic evaluations by Blinded Evaluators

This will be a prospective, multi-arm, evaluator blind, split-face, clinical trial in which subjects will be randomized to 2 groups in 3 separate arms.

1st Arm (n=5) Non-ablative fractionated Thulium laser (Sciton Moxi)

2nd Arm (n=5) Ablative full Erbium:Yag laser (Sciton Contour)

3rd Arm (n=5) Microneedling with RF (Cutera Secret)

In each arm, there will be two groups

1st group: Velez Intense Hydration Facemask on the left side of their face and nothing on the right

2nd group: Velez Intense Hydration Facemask on the right side of their face and nothing on the left side

Both groups will be utilizing the same safety and comfort protocols established by the practice which include the use of topical numbing cream (B.L.T.) before the laser procedure and cleansing with a makeup wipe and alcohol.

After the procedure a blind evaluator will be grading the subjects' erythema, edema, and any side effects. A compliance analysis performed by study coordinator will be done each visit.

Thirty minutes after the laser procedure, digital photography using Canfield's imaging system, and a thermal camera will be done. In addition, a subject questionnaire on satisfaction, erythema, edema and pain levels after the procedure will be completed. Patients will then have the typical post-care treatment on both sides of their face such as Vaseline for laser resurfacing and a hydrating serum for the Moxi and Microneedling. They will apply the mask at home for at least two hours each day and then return to the office daily for questionnaires and photographs until deemed fully healed by the primary investigator.

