6.4 Subject Questionnaires

Subjects will be asked about their satisfaction with the facemask using a subject Satisfaction questionnaire.

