7 ASSESSMENT OF SAFETY

Safety evaluations for this study include an interview of the subjects to obtain information about any medical occurrence that meets the definition of an AE. Each subject should be questioned about AEs at the study visit following the screening visit. The question should be asked: "Since your last clinical visit have you had any health problems?" Information on AEs can also be obtained from signs and symptoms detected during the examination by the evaluator, which should include visual inspection of the treatment area.

AEs must be documented in the source document without regard for cause or relation to investigational product. If in the process of the interview, additional information regarding medical history or preplanned medical or surgical procedures is revealed, it must be documented in the source documents.

It is the responsibility of the Investigator to determine severity of the AE and relatedness of the event to the study product.

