7.5 RECORDING INSTRUCTIONS

Investigators, or other study site personnel, shall record all AEs including:

- a) Event term (recorded in standard medical terminology and avoiding abbreviations)
- b) Affected area
- c) Start date (first day with symptoms)
- d) Stop date (last day with symptoms)
- e) Intensity (mild, moderate, or severe)
- f) Seriousness (serious or not serious)
- g) Causal relationship to study product or study product injection procedure (yes or no)
- h) Action taken (none, medication treatment, non-pharmacological treatment, or other procedures/tests, subject withdrawn)
- i) Outcome of the AE (ongoing, recovered, recovered with sequelae, death, chronic/ stable, not recovered at the end of the study)

All AEs, non-serious as well as serious, are to be reported as an AE. The PI will record all reportable events with start dates occurring any time after informed consent is obtained until 7 (for non---serious AEs) or 14 days (for SAEs) after the last study intervention. At each study visit, the investigator will inquire about the occurrence of AE/SAEs since the last visit. Events will be followed for outcome information until resolution or stabilization.

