8.7 MEASURES TO MINIMIZE BIAS

8.7.1 ENROLLMENT/ RANDOMIZATION/ MASKING PROCEDURES

To avoid bias, the subjects will be randomized to receive the treatment on one side. All evaluators will be blinded as to which side received the active intervention. The blinded evaluators will observe the subjects, but both the evaluator and subjects will be told that no discussions are to take place between the two and that the subjects are to remain silent during the evaluator examination.

To ensure only the clinical investigator performing the procedures and the study coordinator know the assignment, each subject will have an envelope assigned to them to be held by the study coordinator with the subject's name on the outside and the assignment on the inside. Only after the laser treatment does the study coordinator allow the clinical investigator to see the inside of the envelope with the randomized group assignment.

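### Itching is a listed mask risk, but no itch item by cheek is described and section 8.3 has no split by side, so itching may be under-counted and mask itch cannot be separated from procedure itch

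*Combined protocol and SAP*

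**What the plan says.** Section 2.3.1 names itching twice. For the mask: "Potential risk of the mask includes swelling, itching, pain, dermatitis, erythema, or hypersensitivity". For the procedures: "Potential risk of the cosmetic treatments include swelling, itching, pain, dermatitis, erythema, infection, bleeding or scarring".

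On collection, section 3.1 says that at 30 minutes "a subject questionnaire on satisfaction, erythema, edema and pain levels after the procedure will be completed". Section 6.4 (Subject Questionnaires) is narrower: "Subjects will be asked about their satisfaction with the facemask using a subject Satisfaction questionnaire". Neither names itching. Section 3.2.2 specifies a pain rating for each side, and section 7.8 has pain assessed at 30 minutes and at follow-up visits.

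Adverse events are sought by an open question in section 7, "Since your last clinical visit have you had any health problems", and section 7.5 adds: "At each study visit, the investigator will inquire about the occurrence of AE/SAEs since the last visit". Section 7.5 also has the affected area and the intensity recorded for each event. Section 6.3.3, however, words the Day 1-7 recording as participant-reported events on the side that was assigned the mask. At the blinded examination, section 8.7.1 tells evaluator and subject that "no discussions are to take place between the two and that the subjects are to remain silent during the evaluator examination".

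For reporting, section 8.3 plans: "The number and percentage of subjects reporting each post-treatment symptom will be presented in total and by maximum severity". It adds adverse-event summaries counted by subject and by event. Neither part mentions side of face. The first secondary endpoint in section 3.2.2 is the between-side difference in the number of adverse events.

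**The concern.** Itching is felt, not seen, so it is counted only if the subject says so. Pain, erythema and edema have a described rating by the subject; itching has none. If all four appear in one symptom table, the percentages come from different methods of collection and are not like for like. A low itch figure could be read as good tolerability when it partly reflects how the question was put.

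The second problem is attribution. The procedure can cause itching on either cheek. The split-face design supplies the contrast that would isolate the mask's contribution, but a table of subjects without side discards it. Safety and adverse-event incidence with the mask is the first secondary objective, and the mask is reapplied daily until healing, so this bears on what the trial can say about a named mask risk.

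**Working it through.** The plan states no figure on this point, so there is none to reproduce. The check is of the text, followed by illustrations whose inputs are labelled.

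**1. Routes by which itching can enter the data**

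| Route | Prompts for itching? | By cheek? |
|---|---|---|
| Questionnaire (3.1, 6.4) | Not described | Not described for itching |
| Blinded examination (6.3.7, 8.7.1) | No; subject silent, Day 0 only | Not applicable |
| Open question and inquiry at each visit (7, 7.5, 7.6.1) | No | Only through the affected-area field, once volunteered |
| Follow-up recording (6.3.3) | No | Mask side, as worded |

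**2. Attribution, which needs no assumed reporting rate.** Suppose the 8.3 table shows itching in 3 of 15 subjects (20%). The same entry results from each of these cases:
- 3 itch on the masked cheek only: masked minus unmasked = 3 - 0 = +3.
- 3 itch on both cheeks: 3 - 3 = 0.
- 3 itch on the unmasked cheek only: 0 - 3 = -3.

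The table cannot distinguish them.

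**3. Effect of mask-side recording.** If section 6.3.3 is followed literally, the first two cases are both recorded as masked 3, unmasked 0. Procedure itch on both cheeks would then look like a mask effect. This error runs against the mask, whereas under-reporting runs in its favour, so the net direction of a between-side adverse-event count is not clear.

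**4. Possible under-count (assumed inputs).** Let n = 15 (section 8.1), p = true proportion of subjects with itching, and s = share captured by open questioning. Expected number shown = n x p x s; chance that none is shown = (1 - p x s)^n. At p = 20%:

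| s | Expected shown | Chance of none |
|---|---|---|
| 30% | 15 x 0.20 x 0.30 = 0.9 | 0.94^15 = 39.5% |
| 50% | 15 x 0.20 x 0.50 = 1.5 | 0.90^15 = 20.6% |
| 70% | 15 x 0.20 x 0.70 = 2.1 | 0.86^15 = 10.4% |
| 100% | 15 x 0.20 = 3.0 | 0.80^15 = 3.5% |

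Over p = 10% to 40% and s = 30% to 70%, the expected count runs from 0.45 to 4.2, against 1.5 to 6.0 with full capture. The chance of none runs from 63.3% down to 0.7%.

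**5. What by-side data could support.** A two-sided exact sign test on k discordant subjects, all in one direction, gives 2 x 0.5^k: 0.0625 for k = 5 and 0.031 for k = 6. With 15 subjects the result would be descriptive, as section 8.3 intends.

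**The case against.** A reader might infer that subjects are never asked about itching. The documents do not support that. The form itself is not reproduced. The list in section 3.1 is a summary of the 30-minute questionnaire and is evidently incomplete, since section 8.2 compares comfort scores between sides and section 3.1 does not list comfort. Adverse events are asked about at each visit; section 6.3.7 schedules an examination for adverse effects on Day 0 and Days 1-3, then as needed to Day 7; section 7.6.1 allows events to be found from questionnaires; and section 7.5 lets a reported itch be located and graded. The silence rule covers only the blinded examination on Day 0, so subjects may report itching to the investigator or coordinator at any visit.

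The size of any under-count is also fragile. If 3 subjects itch and each has one overall chance of 1/4 to volunteer it, the table shows no itching with probability 0.75^3 = 42%. If 1/4 applied at each of four visits (Day 0 and Days 1-3), with persistent itch and independent reports, it would be 0.75^12 = 3%. Both rest on assumptions outside the documents. Nor does section 8.3 define a post-treatment symptom or say that itching will be a row; it might appear only in the adverse-event summary.

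All of this stands and limits the claim. It does not supply a prompted itch rating by cheek or a split by side in section 8.3. The affected-area field locates an itch that is volunteered but does not prompt one, and section 6.3.3 as worded is narrower than both section 7.5 and the endpoint in section 3.2.2.

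**Conclusion.** The point holds in a limited form. No itch item by cheek is described, and itching would be captured mainly by open questioning, so it may be under-counted relative to pain, erythema and edema. Saying that it will be under-counted goes beyond the documents: no itch rate or reporting probability is given, and the illustrative figures depend wholly on assumed values.

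The attribution problem is firmer. As planned, the 8.3 table cannot separate mask itch from procedure itch, because it has no side split for any symptom and because follow-up recording is worded for the mask side. The missing side split is as much the cause as the missing item, so adding the item alone would not cure it. The primary endpoint and the tested secondary endpoints are unaffected. What is affected is the descriptive safety statement about a named mask risk. The improvement is cheap and worth making before data collection, because itching by cheek cannot be reliably reconstructed afterwards.

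**What to change.** 1. Add one itching item per cheek, on the scale used for the pain item, to the existing subject questionnaire at 30 minutes and at each follow-up visit. If the form already has such an item, name it in the protocol.
2. Reconcile section 6.3.3 with section 3.2.2 so that adverse events are recorded on both sides of the face at every visit.
3. In section 8.3, define the post-treatment symptoms and their source form. Present itching and the other symptoms descriptively by masked and unmasked side within subject, and keep solicited symptoms separate from the adverse-event counts.

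The cost is one questionnaire line per cheek, a by-side layout for the table, and one corrected sentence on recording. No extra visit, staff or procedure is needed, since section 6.3.7 already schedules the questionnaire at these visits. The downside is that solicited itching will be reported more often than volunteered itching, so the safety table may look slightly less favourable.
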